7.4.7. Estimated Glomerular Filtration Rate (eGFR)

Serum creatinine will be measured at the time points specified in Time and Events Schedule in Section 7.1. It will be used to calculate eGFR using the MDRD formula [Levey, 2009], namely:

$$\text{eGFR (ml/min/1.73m}^2\text{)} = 175 \times (\text{serum creatinine})^{-1.154} \times (\text{Age})^{-0.203} \times (0.742 \text{ if female}) \times (1.212 \text{ if African American}).$$

7.4.8. Diabetic Dietary, Exercise, and Home Plasma Glucose Monitoring Advice

Standard diabetic dietary, exercise, and home blood glucose monitoring advice as well as on the signs and symptoms of hypoglycemia and on supplemental oral glucose treatment will be provided at Visit 2 (Week 0) and reinforced at each study site visit through the End of Treatment Visit (Week 26). Subjects should monitor the blood glucose as per the instructions of the investigator and as appropriate for their medical management. The subjects should report promptly, as directed by the investigator, the occurrence of hyperglycemia or hypoglycemia (particularly if symptomatic) to the investigator (or his or her designee). Assessment and action should then occur as deemed appropriate by the investigator.

7.4.9. Hypoglycemic Events

Specific criteria for monitoring hypoglycemic events have been designed to ensure subject safety and to closely monitor hypoglycemia. Hypoglycemic events are defined as follows [Seaquist, 2013]:

Severe Hypoglycemia

- Severe hypoglycemia is an event requiring assistance of another person to actively administer carbohydrates, glucagon, or take other corrective actions. Plasma glucose concentrations may not be available during an event, but neurological recovery following the return of plasma glucose to normal is considered sufficient evidence that the event was induced by a low plasma glucose concentration.

Documented Symptomatic Hypoglycemia

- Documented symptomatic hypoglycemia is an event during which typical symptoms of hypoglycemia are accompanied by a measured plasma glucose concentration ≤ 70 mg/dL (≤ 3.9 mmol/L).

Asymptomatic Hypoglycemia

- Asymptomatic hypoglycemia is an event not accompanied by typical symptoms of hypoglycemia but with a measured plasma glucose concentration ≤ 70 mg/dL (≤ 3.9 mmol/L).

Probable Symptomatic Hypoglycemia

- Probable symptomatic hypoglycemia is an event during which symptoms typical of hypoglycemia are not accompanied by a plasma glucose determination but that was presumably caused by a plasma glucose concentration ≤ 70 mg/dL (≤ 3.9 mmol/L).

Pseudohypoglycemia

- Pseudohypoglycemia is an event during which the person with diabetes reports any of the typical symptoms of hypoglycemia with a measured plasma glucose concentration > 70 mg/dL (> 3.9 mmol/L) but approaching that level.

Any hypoglycemic event, regardless of intensity, that satisfies the definition of an SAE ([Appendix 5](#)) should be categorized as outlined in this section and reported appropriately in the SAE eCRF page and the hypoglycemic events AE of special interest page.

7.5. Tracking of Albiglutide Lyophilized DCC Pen Injector and Liquid Auto-injector Failures and User Errors

All albiglutide lyophilized product DCC pen injector and liquid product auto-injector failures and user errors must be detected, documented, and reported by the investigator throughout the study. Detailed information on DCC pen injector and auto-injector failures and user errors will be collected on the Injector Pen and Auto-injector Failure Reporting Form.

NOTE: Albiglutide lyophilized DCC pen injector and liquid auto-injector failures and user errors associated with or resulting in events fulfilling the definition of an AE or SAE will follow the processes outlined in Section [7.4.1](#).

7.6. Pharmacokinetics

7.6.1. Blood Sample Collection

Blood samples for the determination of albiglutide plasma concentrations will be obtained from all subjects before administration of study treatment according to the Time and Events Table in Section [7.1](#). During visits where ECGs and vital sign measurements are required, blood samples will be collected **after** measurement of ECGs and vital signs.

Blood samples will be collected and stored as detailed in the Laboratory Manual.

7.6.2. Sample Analysis

Plasma analysis will be performed under the control of PTS-DMPK, GlaxoSmithKline, the details of which will be included in the Study Reference Manual (SRM).

Concentrations of albiglutide will be determined in plasma samples using the currently approved bioanalytical methodology. Raw data will be archived at the bioanalytical site (detailed in the SRM).

Once the plasma has been analyzed for albiglutide, any remaining plasma may be analyzed for other compound-related metabolites and the results reported under a separate PTS-DMPK, GlaxoSmithKline protocol.

7.7. Immunogenicity

Serum for antidrug antibody testing will be obtained from all subjects before administration of study treatment at week 0, 2, 4, 8, 12, 16, 20, 24, 26 and at follow-up (wk 34, if applicable), according to the Time and Events Table in Section 7.1

The presence of anti-albiglutide antibodies will be assessed using a validated enzyme-linked immunosorbent assay. The assay involves screening, confirmation, and titration steps (tiered-testing approach). Confirmed positive samples will be titrated to obtain the titre of antibodies and tested for GLP-1 and albumin cross-reactivity, as well as for albiglutide neutralizing activity. Samples positive for both anti-GLP-1 antibodies and drug neutralizing antibodies may be tested for GLP-1 neutralizing activity ([Appendix 7](#)).

Additionally, in the case of severe allergic reactions that include anaphylaxis, angioedema, or other severe potential hypersensitivity reactions, three 1-mL serum samples should be obtained for immunogenicity testing (within 24 hours of the event if possible) and sent to the central laboratory (see details in the SRM) for immediate distribution to a contracted testing facility for specific immunological testing (albiglutide-specific IgE and other tests, as appropriate) A follow-up serum sample will be collected 8 weeks after the final dose of study treatment in the case of early withdrawal from the study.

For subjects who have discontinued study treatment or subjects who have completed the 26 week treatment period, but do not consent and/or are not eligible to participate in the 26 week extension study (Study 204682), if baseline antibody levels or a reduction in titer are not achieved by the follow-up visit then additional samples for immunogenicity testing may be obtained every 30 days following the follow-up visit until baseline antibody levels, or reduced titres, are achieved. Subjects eligible for the extension study (Study 204682) will have immunogenicity samples taken as specified in protocol 204682.

7.8. Genetics

Information regarding genetic research is included in [Appendix 4](#).

8. DATA MANAGEMENT

For this study, subject data will be entered via an eCRF into Oracle Clinical Remote Data Capture (OC RDC) system. Subject data will be available for viewing through access to the OC RDC system. Data provided from other sources will be received, reconciled, combined and transferred to GSK at predetermined time points.

Management of clinical data will be performed in accordance with applicable PPD standards and data cleaning procedures to ensure the integrity and quality of the data, e.g., removing errors and inconsistencies in the data. Adverse events and concomitant medication terms will be coded using the Medical Dictionary for Regulatory Activities (MedDRA) and a validated medication dictionary GSKDrug.

The eCRFs (including queries and audit trails) will be sent at the end of the study in CD format to GSK to be retained. Each investigator will receive a copy of their site specific data in the same format to maintain as the investigator copy. In all cases, subject initials will not be collected or transmitted.

9. STATISTICAL CONSIDERATIONS AND DATA ANALYSES

9.1. Hypotheses

The primary hypothesis is to test that liquid drug product will provide glycemic control (as measured by HbA1c change from baseline) non-inferior to lyophilized drug product for a period of 26 weeks of treatment in subjects with T2DM.

9.2. Sample Size Considerations

9.2.1. Sample Size Assumptions

This study will randomly assign approximately 150 subjects to each of the 2 treatment groups (liquid drug product and lyophilized drug product) in a 1:1 ratio, for a total of approximately 300 subjects. Eligible subjects will be stratified by age (<65 or ≥65 years of age), weight (<90 kg or ≥90 kg), and background antidiabetic therapy (diet and exercise or stable dose of metformin).

With 133 subjects in each of the 2 treatment groups, the study will provide 90% power to demonstrate non-inferiority for HbA1c change from baseline, assuming a non-inferiority margin of 0.4%, an expected treatment group difference of 0.0%, and a common standard deviation of 1%, using a 2-sample, 1-sided t test with significance level of 0.025. Power was calculated using PASS [Hintze, 2013]. Assuming that 13% of subjects will be withdrawn early or will be lost to follow-up; therefore, approximately 150 subjects will be randomized in each treatment group.

[figure not shown]
The non-inferiority margin of 0.40 was selected based on the expected effect of the albiglutide lyophilized drug product as active control. Results from two HARMONY

Phase III studies (subset of GLP112756 and GLP112753) for the comparison of the control albiglutide lyophilized drug product versus placebo were used in selecting the non-inferiority margin. The two studies are similar to the current study in terms of the population and the design; subjects were either on diet and exercise or metformin background therapy and received 30 mg of albiglutide then up-titrated to 50 mg albiglutide. The 95% confidence interval from the 2 Harmony studies for HbA_{1c} change from baseline at week 24 for albiglutide lyophilized drug product difference from placebo is (-1.04, -0.75). The conservative effect in terms of the difference from placebo for HbA_{1c} change from baseline at Week 24 for albiglutide lyophilized drug product versus placebo is 0.75% (M1 =0.75%, as defined in Guidance for Industry: Non-Inferiority Clinical Trials [FDA, 2010]). M2, calculated as 50% of M1 is 0.375 (approximately 0.4). The margin of 0.40% that should be met in this trial will preserve at least 45% of the effect of the comparator and it is below M1.

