9.4. Key Elements of Analysis Plan

9.4.1. Primary Analyses

The primary endpoint is the change from baseline in HbA1c at Week 26. The primary analysis will include all HbA1c values collected at scheduled visits up to Week 26. This will include values after hyperglycemia rescue and discontinuation from investigational product. The primary analysis of the primary endpoint will be conducted using a mixed-effect model with repeated measures (MMRM) in the ITT Population. MMRM will use all available data. Imputation under the non-inferiority null hypothesis for missing data will be incorporated [Koch, 2008]. Multiple imputation will be used to replace missing data of change from baseline of HbA1c at Week 26 for all patients in both treatment arms as a first step, and then to make all the imputed values for the liquid drug product arm worse by the non-inferiority margin 0.4.

Multiple imputation approach uses separate covariance parameter estimation for each arm, and also separate regression parameters are estimated on baseline covariates within each arm. For subjects with missing data the imputation will use means and variances-covariances from subjects in that treatment group where that subject with missing data belongs. This approach will be used for all data missing post withdrawal due to lost to follow-up or withdraws consent.

Non-inferiority testing will be performed at a one-sided alpha of 0.025 and non-inferiority margin of 0.4.

Further details of the imputation method for the primary analysis will be provided in the RAP.

The primary MMRM model will include HbA1c change from baseline at all post-baseline visits as dependent variables; treatment, region, age category, weight, background antidiabetic therapy, visit week, and treatment-by-week interaction as fixed effects; baseline HbA1c as a continuous covariate; and subject as a random effect. Treatment effects estimates (and associated CI) of albiglutide liquid drug product will be evaluated within this MMRM model as least squares means contrasts relative to the lyophilized drug product. An unstructured covariance matrix will be used for the MMRM analysis, unless the model does not converge, in which case the covariance matrix will be decided upon model convergence status and the Akaike information criterion.

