7.1.1.1. Primary Analysis on Primary Efficacy Endpoint

The primary endpoint is the change from baseline in HbA_{1c} at Week 26. The primary analysis of the primary endpoint will be conducted using a mixed-effect model with repeated measures (MMRM) in the ITT Population. The primary analysis will include all HbA_{1c} values collected at scheduled visits from Week 4 up to Week 26. This will include values after hyperglycemia rescue and discontinuation from investigational product. Imputation under the non-inferiority null hypothesis for missing data will be incorporated [Koch, 2008]. Multiple imputation assuming missing at random (MAR) will be used to replace missing data of change from baseline of HbA_{1c} at Week 26 for all subjects in both treatment arms as a first step, and then to make all the imputed values for the liquid drug product arm worse by the non-inferiority margin 0.4.

Multiple imputation approach under MAR uses separate means and variance-covariance parameter estimation for each treatment arm (Carpenter and Kenward, 2013). Missing values for each subject will be imputed multiple times based on his or her own observed HbA_{1c} change from baseline values available and also based on the estimated means and variance-covariance from the treatment group where that subject is randomized to. This approach will be used for all missing data at Week 26 due to any reason including, but not limited to lost to follow-up and withdrawal consent. The details of implementing this multiple imputation approach are the following:

- **Step 1a:** Missing values at Week 26 will be imputed 100 times via SAS PROC MI (specifying BY treatment group, using MCMC statement with the option chain = multiple, including baseline and all post-baseline scheduled visits up to Week 26). As a result, 100 imputed datasets will be generated. Note: Only imputed values at Week 26 will be retained while the imputed values at other visits will be dropped from the imputed datasets.
- **Step 1b:** For each of the 100 imputed datasets from Step 1 the imputed values at Week 26 for the liquid drug product arm will be increased by 0.4.
- **Step 2:** Apply MMRM analysis as specified below for each of the 100 imputed dataset and save LSmeans (standard error) for each treatment arm at Week 26 and difference in LSmeans between treatment groups (standard error) from each of the 100 analyses.

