11.12. Appendix 12: Sample Size Considerations

11.12.1. Sample Size Assumptions

[figure not shown]
[figure not shown]
This study will randomly assign approximately 150 subjects to each of the 2 treatment groups (liquid drug product and lyophilized drug product) in a 1:1 ratio, for a total of approximately 300 subjects. Eligible subjects will be stratified by age (<65 or ≥65 years of age), weight (<90 kg or ≥90 kg), and background antidiabetic therapy (diet and exercise or stable dose of metformin).

With 133 subjects in each of the 2 treatment groups, the study will provide 90% power to demonstrate non-inferiority for HbA1c change from baseline, assuming a non-inferiority margin of 0.4%, an expected treatment group difference of 0.0%, and a common standard deviation of 1%, using a 2-sample, 1-sided t test with significance level of 0.025. Power was calculated using PASS [Hintze, 2013]. Assuming that 13% of subjects will be withdrawn early or will be lost to follow-up; therefore, approximately 150 subjects will be randomized in each treatment group.

The non-inferiority margin of 0.40 was selected based on the expected effect of the albiglutide lyophilized drug product as active control. Results from two HARMONY Phase III studies (subset of GLP112756 and GLP112753) for the comparison of the control albiglutide lyophilized drug product versus placebo were used in selecting the non-inferiority margin. The two studies are similar to the current study in terms of the population and the design; subjects were either on diet and exercise or metformin background therapy and received 30 mg of albiglutide then up-titrated to 50 mg albiglutide. The 95% confidence interval from the 2 Harmony studies for HbA1c change from baseline at week 24 for albiglutide lyophilized drug product difference from placebo is (-1.04, -0.75). The conservative effect in terms of the difference from placebo for HbA1c change from baseline at Week 24 for albiglutide lyophilized drug product versus placebo is 0.75% (M1 =0.75%, as defined in Guidance for Industry: Non-Inferiority Clinical Trials [FDA, 2010]). M2, calculated as 50% of M1 is 0.375 (approximately 0.4). The margin of 0.40% that should be met in this trial will preserve at least 45% of the effect of the comparator and it is below M1.

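### The stated 90% power leaves out the 0.4 penalty on imputed liquid-arm values; on the plan's own assumptions the primary analysis has about 80%

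*Protocol*

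**What the plan says.** Protocol 9.2.1 gives the power claim: "With 133 subjects in each of the 2 treatment groups, the study will provide 90% power to demonstrate non-inferiority for HbA1c change from baseline". Its inputs are "assuming a non-inferiority margin of 0.4%, an expected treatment group difference of 0.0%, and a common standard deviation of 1" (percentage point), "using a 2-sample, 1-sided t test with significance level of 0.025". Loss of subjects is used only to raise the number randomised: "Assuming that 13% of subjects will be withdrawn early or will be lost to follow-up; therefore, approximately 150 subjects will be randomized" per arm. SAP 11.12.1 repeats the claim: "With 133 subjects in each of the 2 treatment groups, the study will provide 90% power". The sensitivity sections (Protocol 9.2.2, SAP 11.12.2) vary the SD from 0.7 to 1.2 and keep 133 per arm and a zero difference.

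The primary analysis does not discard subjects without a Week 26 value. Protocol 9.4.1 imputes them in both arms and then says to "make all the imputed values for the liquid drug product arm worse by the non-inferiority margin 0.4". SAP 7.1.1.1, Step 1b, is to the same effect: "the imputed values at Week 26 for the liquid drug product arm will be increased by 0.4". The SAP applies this to Week 26 values missing for any reason. Non-inferiority is concluded if the upper limit of the two-sided 95% confidence interval is at most 0.4.

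Neither sample-size section mentions the penalty.

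**The concern.** The power calculation and the primary analysis treat the same 13% of subjects in incompatible ways. The calculation removes them and compares the rest. The analysis keeps them and, in the liquid arm, shifts each by the full margin towards inferiority. The estimated difference is then biased against the liquid product even when the products are identical.

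The amendment history (Protocol Appendix 9) explains how this arose. Before Amendment 2 the primary analysis was an MMRM without imputation, assuming data missing at random, and a t test on evaluable subjects approximates that well. Amendment 2 added the penalised imputation, and its list of changes contains none to the sample-size section.

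The power figure justifies enrolling about 300 subjects, and it governs how a failed result is read. At 80% power, failure is much weaker evidence against the liquid product than a reader would infer from 90%. No sample-size re-estimation is planned, so nothing later in the plan corrects the figure.

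**Working it through.** **Inputs.** Margin 0.4, true difference 0, SD 1.0, one-sided alpha 0.025, about 150 randomised per arm and 13% loss (Protocol 9.2.1, SAP 11.12.1); +0.4 on imputed liquid-arm values (Protocol 9.4.1, SAP 7.1.1.1). The documents give no correlation between visits, so I assume a range.

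**Step 1: reproduce the stated figure.** SE = SD x sqrt(2/n) = sqrt(2/133) = 0.1226. Noncentrality = 0.4/0.1226 = 3.26. The noncentral t distribution on 264 df gives 90.1%. The stated figure is right for the stated test.

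**Step 2: evaluable number.** 150 x 0.87 = 130.5, not 133. (133/0.87 = 153, whereas 133 x 1.13 = 150.) With 130.5 per arm, SE = 0.1238, noncentrality = 3.23 and power is 89.6%. This costs about half a point.

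**Step 3: add the penalty.** With identical products and a proportion m missing, the expected estimate is m x 0.4 = 0.13 x 0.4 = 0.052. The distance left to the margin is 0.4 - 0.052 = 0.348.

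- If earlier visits carry no information about Week 26, imputation recovers nothing and the SE is that of 130.5 observed per arm. Noncentrality = 0.348/0.1238 = 2.81, power **80.0%**.
- If imputation lost no information at all, the SE is that of 150 per arm, 0.1155. Noncentrality = 0.348/0.1155 = 3.01, power **85.2%**. This is a ceiling.

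**Step 4: simulation.** 150 per arm, 13% missing at random, imputation within arm (50 imputations), +0.4 in the liquid arm, Rubin's rules, 4,000 trials per row, no covariate adjustment:

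| Correlation of earlier HbA1c with Week 26 (assumed) | Power without penalty | Power with penalty |
|---|---|---|
| 0 | 89.7% | 79.7% |
| 0.5 | 89.7% | 80.5% |
| 0.7 | 91.2% | 81.4% |
| 0.9 | 92.5% | 83.4% |

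The Monte Carlo standard error near 80% is about 0.6 points (sqrt(0.8 x 0.2/4000)).

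**Step 5: dependence on missing rate and SD.** By t test with 150(1 - m) observed per arm and distance 0.4(1 - m):

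| Missing at Week 26 | Without penalty | With penalty |
|---|---|---|
| 5% | 92.0% | 89.2% |
| 10% | 90.6% | 83.8% |
| 13% | 89.6% | 80.0% |
| 15% | 88.9% | 77.2% |
| 20% | 87.0% | 69.5% |

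At 13% missing with the penalty, SD 0.9 gives about 88% and SD 1.1 about 72%. On the basis of the plan's own figure (133 per arm, no penalty), SD 1.1 gives about 84%.

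**The case against.** **Covariates.** The planned model adjusts for baseline HbA1c, its interaction with week, region and the stratification factors, whereas the steps above use SD 1.0 unadjusted. If SD 1.0 is the raw SD of the change, adjustment would lower it. The residual SD is sqrt(1 - r^2) for an assumed correlation r between baseline and change, so r = 0.3, 0.4 and 0.5 give 0.95, 0.92 and 0.87. Power with the penalty is then roughly 83 to 84%, 86 to 88% and 89 to 91%. This stands as a reason to show a range. It does not rescue the stated figure: the plan claims no such gain, gives no correlation, and does not say whether 1.0 is raw or residual. The same gain would also raise the power without the penalty, so the penalty would still cost power.

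**Retention.** The 13% is described as early withdrawal or loss to follow-up, while subjects who stop treatment now stay in the study and are expected at Week 26. Missingness could be well below 13%, and at 5% power is back to about 89%. This also stands as a scenario. But 13% is the only loss figure in either document, and it is what turns 133 into 150. If the sponsor now expects less, the sample-size section should say so.

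**Conservatism.** The penalty does not inflate type I error. With a true difference of 0.4 and data missing at random, the expected estimate is 0.452. The SAP also plans an MMRM without imputation as a supportive analysis and a nine-scenario tipping-point analysis. All of this is correct, but the point here is the power statement, not the validity of the test.

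**Nature of the error.** The quoted sentence contains no slip of arithmetic; it gives the power of a test that is not the primary one. The shortfall from 133 to 130.5 is a half-point detail.

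**Conclusion.** The concern holds. With SD 1.0, a true difference of 0, 150 per arm and 13% missing at Week 26, the pre-specified primary analysis has about 80% power (80% to 83% over assumed visit correlations of 0 to 0.9, with a ceiling of 85.2%), against 90% stated. Almost all of the loss of about 10 points comes from the penalty. For identical products, the risk of missing non-inferiority roughly doubles, from 1 in 10 to 1 in 5. The 90% figure would need Week 26 missingness of about 4 to 5% or less, or a residual SD of about 0.87 at 13% missing; the plan states neither. The SD sensitivity figure has the same defect. The consequence is for power and for the reading of a failed result; type I error is not inflated.

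**What to change.** In Protocol 9.2.1 and SAP 11.12.1, state the power of the planned analysis: with 150 per arm, SD 1.0 and 13% missing, the expected estimate under identical products is 0.052 and power is about 80% (79% to 83% depending on within-subject correlation). Pair that statement with the 130 evaluable per arm that 150 x 0.87 gives. The 133 and 90% may stay only if labelled as a complete-data t test. Say whether SD 1.0 is a raw or a residual SD; if a covariate gain or a lower missing rate is expected, give the value assumed.

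Redraw the figure in Protocol 9.2.2 and SAP 11.12.2 as power against SD and missing rate (0 to 15%) with the +0.4 imputation applied.

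The cost is wording and one recomputed figure, and the stated power becomes less favourable. The analysis, margin and decision rule stay as they are, and no extra patients are requested. For scale, regaining 90% at 13% missing would take about 201 randomised per arm (201 x 0.87 = 175 observed).

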9.2.2. Sample Size Sensitivity

Figure 2 illustrates the power versus standard deviation of 0.7, 0.8, 0.9, 1.0, 1.1, and 1.2 to reject the null hypothesis of inferiority for HbA_{1c} change from baseline, assuming a non-inferiority margin of 0.4%, an expected treatment group difference of 0.0%, and a sample size of 133 per treatment group, using a 2-sample, 1-sided t- test with a significance level of 0.025.

Figure 2 Power of non-inferiority testing for HbA_{1c} different values of Standard Deviations (S1) of 0.7, 0.8, 0.9, 1.0, 1.1, and 1.2

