2.4. Statistical Hypotheses

The primary hypothesis to be tested is that the liquid drug product will provide glycemic control (as measured by HbA_{1c} change from baseline) non-inferior to the lyophilized drug product for a period of 26 weeks of treatment in subjects with T2DM.

- The null hypothesis is that the difference in the mean change from baseline to Week 26 in HbA_{1c} between the liquid drug product and the lyophilized drug product is greater than the non-inferiority margin of 0.4%.

- The alternative hypothesis is that the difference in the mean change from Baseline to Week 26 in HbA_{1c} between the liquid drug product and the lyophilized drug product is less than or equal to the non-inferiority margin of 0.4%.
- The null hypothesis will be tested based on the upper bound of 1-sided 97.5% confidence interval (equivalently, the upper bound of a 2-sided 95% confidence interval) of the least squares mean of the treatment difference estimated from a MMRM model. The MMRM model will include HbA_{1c} change from baseline as the dependent variable; treatment, region (defined in [Appendix 8: Multicenter](#)), age category (<65 or ≥65 years), weight category (<90 or ≥90 kg), background antidiabetic therapy (diet and exercise or stable dose of metformin), visit week, treatment-by-week interaction and baseline HbA_{1c}-by-week interaction as fixed effects; baseline HbA_{1c} as a continuous covariate; and subject as a random effect. An unstructured covariance matrix will be used for the MMRM analysis, unless the model does not converge, in which case the covariance matrix will be decided upon model convergence status and the Akaike information criterion. If the upper bound of 1-sided 97.5% confidence interval is less than or equal to 0.4%, non-inferiority will be concluded.

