- **Step 3:** Combine the 100 set of analysis results using Rubin's rules (Rubin, 1987) via SAS PROC MIANALYZE. The treatment differences, confidence intervals and p-values will be estimated by MODELEFFECTS and STDERR statement. Use the degrees of freedom (EDF) you would have if the dataset were complete.

The MMRM model via PROC MIXED will include HbA_{1c} change from baseline at post-baseline scheduled visits from Week 4 up to Week 26 as dependent variables; treatment, region (defined in [Appendix 8: Multicenter](#)), age category (<65 or ≥65 years), weight category (<90 or ≥90 kg), background antidiabetic therapy (diet and exercise or stable dose of metformin), visit week, treatment-by-week interaction and baseline HbA_{1c}-by-week interaction as fixed effects; baseline HbA_{1c} as a continuous covariate; and subject as a random effect. An unstructured covariance matrix will be used for the MMRM analysis, unless the model does not converge, in which case the covariance matrix will be decided upon model convergence status and the Akaike information criterion. Treatment effects estimates (and associated CI) of albiglutide liquid drug product will be evaluated within this MMRM model as least squares means contrasts relative to the lyophilized drug product.

The null hypothesis will be tested based on the 1-sided 97.5% confidence interval (with upper bound, equal to that of 2-sided 95% confidence interval) of the treatment difference at Week 26, which is estimated from the multiple imputation/MMRM (i.e. combined MMRM results from multiple imputation). If the upper bound of the confidence interval is less than or equal to 0.4%, non-inferiority will be concluded.

In addition, the observed HbA_{1c} and change from baseline HbA_{1c} will be summarized descriptively and presented graphically.

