11.14.3. Efficacy Tables

Efficacy: Tables					
No.	Population	IDSL / TST ID / Example Shell	Title	Programming Notes	Deliverable [Priority]
HbA1c					
2.1.	ITT		Primary Analysis - Analysis of Change from Baseline in HbA1c (%) at Week 26 — With Imputation		
2.2.	ITT		Statistical Output Supporting the Primary Analysis of Change from Baseline in HbA1c (%) at Week 26		
2.3.	ITT		Supportive Analysis 1 - Analysis of Change from Baseline in HbA1c (%) at Week 26 — Without Imputation		
2.4.	ITT		Statistical Output Supporting the Supportive Analysis 1 of Change from Baseline in HbA1c (%) at Week 26 — Without Imputation		
2.5.	ITT		Supportive Analysis 2 - Analysis of Change from Baseline in HbA1c (%) at Week 26 — Without Imputation and Excluding Data after Hyperglycemia Rescue and discontinuation from study treatment		
2.6.	ITT		Statistical Output Supporting the Supportive Analysis 2 of Change from Baseline in HbA1c (%) at Week 26 — Without Imputation and Excluding Data after Hyperglycemia Rescue and discontinuation from study treatment		
2.7.	PP		Supportive Analysis 3 — Per Protocol Analysis of Change from Baseline in HbA1c (%) at Week 26 — Without Imputation		
2.8.	PP		Statistical Output Supporting the Supportive Analysis 3 of Per Protocol Analysis of Change from Baseline in HbA1c (%) at Week 26 — Without Imputation		

Efficacy: Tables					
No.	Population	IDSL / TST ID / Example Shell	Title	Programming Notes	Deliverable [Priority]
2.9.	ITT		Subgroup analysis: Analysis of Change from Baseline in HbA1c (%) at Week 26 by Baseline HbA1c Category — With Imputation		
2.10.	ITT		Subgroup analysis: Analysis of Change from Baseline in HbA1c (%) at Week 26 by Age Category at Randomization — With Imputation		
2.11.	ITT		Subgroup analysis: Analysis of Change from Baseline in HbA1c (%) at Week 26 by Region — With Imputation		
2.12.	ITT		Subgroup analysis: Analysis of Change from Baseline in HbA1c (%) at Week 26 by Weight Category at Randomization — With Imputation		
2.13.	ITT		Subgroup analysis: Analysis of Change from Baseline in HbA1c (%) at Week 26 by Background Antidiabetic Therapy — With Imputation		
2.14.	ITT		Subgroup analysis: Analysis of Change from Baseline in HbA1c (%) at Week 26 by Gender — With Imputation		
2.15.	ITT		Subgroup analysis: Analysis of Change from Baseline in HbA1c (%) at Week 26 by Race — With Imputation		
2.16.	ITT		Subgroup analysis: Analysis of Change from Baseline in HbA1c (%) at Week 26 by Ethnicity — With Imputation		

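### Does calling M2 = 0.375 approximately 0.4 undermine the 0.40 non-inferiority margin?

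*Protocol*

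**What the plan says.** Protocol 9.2.1 bases the margin on two earlier phase III studies of the lyophilized product. The 95% confidence interval for "albiglutide lyophilized drug product difference from placebo is (-1.04, -0.75"), and the limit nearest zero gives M1 = 0.75. The text goes on: "M2, calculated as 50% of M1 is 0.375 (approximately 0.4"). The next sentence describes the margin actually adopted: "The margin of 0.40% that should be met in this trial will preserve at least 45% of the effect of the comparator", and adds that it lies below M1. SAP 11.12.1 repeats all of this.

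The value used everywhere else is 0.4. Protocol 9.4.1 has "Non-inferiority testing will be performed at a one-sided alpha of 0.025 and non-inferiority margin of 0.4". SAP 2.4 has "If the upper bound of 1-sided 97.5% confidence interval is less than or equal to 0.4%, non-inferiority will be concluded", and SAP 7.1.1.1 gives the same rule for the combined multiple-imputation result.

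**The concern.** Half of 0.75 is 0.375, and the decision rule is a sharp cut at 0.40. The plan therefore derives a margin from a 50% rule and then tests against a larger number. Two consecutive sentences carry two retention figures (50%, then at least 45%), and 0.40 meets only the second. No reason is given for accepting less than half, and being below M1 is not one, since every value under 0.75 satisfies it.

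The possible harm is a misreading. A trial whose upper bound fell above 0.375 but not above 0.40 would be declared non-inferior, and someone who stopped at the M2 sentence might think half of the comparator effect had been shown to be preserved. This is the trial's only formal test, so the basis of its threshold matters.

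**Working it through.** **Inputs.** From Protocol 9.2.1: historical CI (−1.04, −0.75), M1 = 0.75, margin 0.40, true difference 0, SD 1, one-sided alpha 0.025, 133 evaluable per arm, 90% power, 13% dropout, about 150 randomized per arm. From Protocol 9.2.2: SD range 0.7 to 1.2. From SAP 7.1.1.1: 0.4 is added to imputed Week 26 values in the liquid arm.

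**The plan's own figures.**
- M2 = 0.5 × 0.75 = 0.375, as printed. To one decimal this is 0.4.
- Retention at 0.40 = 1 − 0.40/0.75 = 46.7%, which meets the stated floor of 45%. Exactly 45% would correspond to 0.55 × 0.75 = 0.4125.
- Sample size by the noncentral t at 0.40: 133 per arm, power 90.1%. With 13% dropout, 133/0.87 = 153, consistent with about 150.

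Every printed figure reproduces, and the sample size is the one for 0.40.

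**Size of the gap.** 0.40 − 0.375 = 0.025 points, or 0.025/0.375 = 6.7% of M2. In retention it is 50 − 46.7 = 3.3 percentage points of M1.

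**How often a result lands in the gap.** At 133 per arm and SD 1, SE = √(2/133) = 0.1226 and t(0.975, 264) = 1.969, so the CI half-width is 0.241. Passing at 0.40 needs an observed difference of at most 0.159; a bound at or below 0.375 needs at most 0.134. With a true difference of 0 (differences taken before rounding):

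| SD | Bound ≤ 0.40 | Bound ≤ 0.375 | In between |
|---|---|---|---|
| 0.7 | 99.6% | 99.2% | 0.5% |
| 0.8 | 98.2% | 96.8% | 1.5% |
| 0.9 | 95.1% | 92.3% | 2.8% |
| 1.0 | 90.1% | 86.1% | 4.0% |
| 1.1 | 84.0% | 79.1% | 4.9% |
| 1.2 | 77.3% | 71.9% | 5.4% |

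**Error rates.** With complete data and 133 per arm, a true loss of 0.40 passes 2.50% of the time, so alpha is exact for the stated null. A true loss of 0.375 passes 3.95% of the time.

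**With the planned imputation.** Assume 150 per arm, SD 1, the same missing fraction f in both arms, data missing at random before the penalty, and no gain from covariates or earlier visits. The estimate shifts by 0.4f and SE = √(2/(150(1 − f))).

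| f | Bound in (0.375, 0.40], true difference 0 | Pass at 0.40 if true loss is 0.375 |
|---|---|---|
| 0 | 3.3% | 4.06% |
| 6.25% | 4.7% | 2.50% |
| 13% | 6.1% | 1.47% |

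At f = 6.25% the shift is 0.4 × 0.0625 = 0.025, exactly the amount by which 0.40 exceeds M2. Above that fraction, the imputation more than offsets the rounding.

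**The case for a change.** The strongest case for a change is that the 50% rule is the only derivation the plan offers, while the 45% figure merely describes a margin already chosen. M2 is given to three decimals and the decision rule is exact, so rounding is a weak justification. With little missing data, a true loss of half of M1 passes about 4% of the time rather than 2.5%. A cheap remedy seems available: reword the sentence, report with SAP Table 2.1 the retention implied by the observed bound (1 − bound/0.75), and speak of 50% preservation only if that bound is 0.375 or less.

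The first part stands as a comment on drafting: 0.40 does not satisfy a 50% rule, and the documents do not say why less was accepted. The rest does not carry the point further. The 4% figure is the error rate for a null of 0.375, which the plan never tests. The retention actually achieved is disclosed in the very next sentence, so a reader of the whole paragraph is not misled.

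A line in Table 2.1 would guard against a 50% claim that nobody makes. It would also be hard to read, because the primary bound includes the imputation penalty. At 13% missing the penalty is 0.4 × 0.13 = 0.052, and 0.052/0.75 is about 7 percentage points of M1, twice the 3.3-point gap. A shortfall from 50% could then reflect missing data rather than the product.

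Lowering the margin to 0.375 would be a real change, but a costly one: 151 evaluable per arm for 90% power, hence 151/0.87 = 174 randomized per arm and about 348 in total, to move the threshold by 0.025. M1 is already a cautious anchor. If the CI midpoint, (1.04 + 0.75)/2 = 0.895, is taken as the point estimate (an assumption, as none is printed), 0.40 retains 1 − 0.40/0.895 = 55%.

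**Conclusion.** No change to the plan is needed. The word approximately is loose, since 0.40 is 0.025 above half of M1 and preserves 46.7% of it. Even so, no printed figure is false: M2 is shown unrounded, the stated floor of 45% is correct, and no objective or decision rule promises 50%. The test, alpha, sample size and power are all consistent with 0.40.

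If the products are equal, about 4.0% of trials at SD 1.0 and 133 per arm would have a bound between 0.375 and 0.40 (0.5% to 5.4% over the plan's SD range). Those are correct passes under the stated rule. At the planned 13% dropout, a true loss of 0.375 would pass about 1.5% of the time, under the simple missing-data assumptions given above; with almost no missing data it would be about 4%. Anyone editing the documents for another reason could state 46.7% outright, but that would alter neither what the trial does nor what it concludes.
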